11.2 DISPOSITION OF PATIENTS

Screened patients are defined as any patient who met the inclusion criteria and signed the informed consent.

Patients treated without being randomized will not be considered as randomized and will not be included in any efficacy population.

For any patient randomized more than once, only the data associated with the first randomization will be used in any analysis population. The safety experience associated with any later randomization will be assessed separately.

The safety experience of patients treated and not randomized will be reported separately, and these patients will not be in the safety population.

11.3 ANALYSIS POPULATIONS

11.3.1 Efficacy populations

11.3.1.1 Modified intent-to-treat population

The primary population for analysis will be the modified ITT (mITT) population: ITT population with an evaluable primary endpoint. This will consist of all patients who receive at least 1 injection of investigational medicinal product, have a valid baseline % predicted FVC measurement, and have at least one post-baseline % predicted FVC measurement.

11.3.2 Safety population

Safety population - the population considered for the safety analysis will be the as-treated population defined as randomized population who did actually receive at least 1 dose or part of a dose of IMP analyzed according to the treatment actually received.

In addition:

- Non randomized but treated patients will not be part of the safety population, but their safety data will be presented separately.
- Randomized patients for whom it is unclear whether they took the study medication will be included in the safety population as randomized.
- For patients receiving more than 1 study treatment during the trial, the treatment group allocation for as-treated analysis will be the one received at the majority of injections

11.3.3 Pharmacokinetic analysis population

The population for all PK and ADA analysis will be all randomized and treated patients having at least one sample.

11.4 STATISTICAL METHODS

11.4.1 Extent of study treatment exposure and compliance

The extent of study treatment exposure and compliance will be assessed and summarized by actual treatment received within the safety population.

11.4.1.1 Extent of investigational medicinal product exposure

Duration of IMP exposure is defined as: last dose date – first dose date + 14 days, regardless of unplanned intermittent discontinuations.

11.4.1.2 Compliance

A given administration will be considered noncompliant if the patient did not take the planned dose of treatment as required by the protocol. No imputation will be made for patients with missing or incomplete data.

Treatment compliance, above-planned and under-planned dosing percentages will be summarized descriptively (N, Mean, SD, Median, Min, and Max). The percentage of patients with compliance <80% will be summarized. In addition, number and percentage of patients with at least 1 above-planned dosing administration will be given, as well as the number and percentage of patients with 0, (0, 20%), and >20% under-planned dosing administrations.

11.4.2 Analyses of efficacy endpoints

11.4.2.1 Analysis of primary efficacy endpoint(s)

Due to the non-normality of the endpoint distribution, a two-sided rank-based analysis of covariance (rank ANCOVA) model adjusted for baseline, will be used to compare the primary efficacy variable between each active treatment group and placebo:

Change from baseline in the % predicted FVC at Week 52

The rank ANCOVA will be performed as follows:

1. The first step of the analysis is to compute the standardized ranks of the response variable (change from baseline in % predicted FVC at Week 52) and covariate (baseline % predicted FVC)
2. The second step is to perform the ANCOVA analysis based upon these ranks. Within the ANCOVA each active treatment group will be compared to placebo using a contrast.

In the primary analysis, Week 52 assessments will be used regardless of whether the patient has previously discontinued treatment. For patients with missing data at week 52, the week 52 value will be estimated based on a linear regression using all available % predicted FVC measurements. Predicted changes greater than zero (increases above baseline) will be set to zero. For patients with no Week 52 value due to the patients death (or transplant), the value for analysis will be assigned the lowest (worst) rank. Sensitivity analyses including an analysis of the on-treatment data only will be described in the statistical analysis plan.

11.4.2.2 Analyses of secondary efficacy endpoints

Disease progression, defined as decrease in absolute % predicted FVC $\geq 10\%$, or decrease in absolute % predicted DLCO $\geq 15\%$, or lung transplant, or death will be analyzed as a time to event variable. Patients not meeting the definition for disease progression will be considered censored at the time of their week 52 FVC assessment. For patients with a missing FVC assessment at week 52 the censoring time will be the time of the last measured FVC or DLCO assessment.

The time to disease progression will be compared between each active group and placebo using a log-rank test. The hazard ratio compared to placebo will be estimated from a Cox proportional hazards model.

The incidence of all-cause mortality will be calculated, but no hypothesis testing will be performed for this endpoint.

11.4.2.3 Multiplicity considerations

The overall type I error rate for this study is 5%. A hierarchical testing procedure will be used to control the type I error over the two doses. The qw dose group will be compared to placebo first, and only if this comparison is significant will the q2w dose group be compared to placebo.

The same procedure will be used for the disease progression endpoint if significance is achieved for both doses on the primary endpoint.

11.4.3 Analyses of safety data

The summary of safety results will be presented by treatment group on the basis of the safety population.

All safety analyses will be performed on the safety population using the following common rules:

- The baseline value is defined generally as the last available value before randomization.
- For quantitative safety parameters based on central laboratory/reading measurements, descriptive statistics will be used to summarize results and change from baseline values by visit and treatment group.
- The analysis of the safety variables will be essentially descriptive and no hypothesis testing is planned.

The following definitions will be applied to laboratory parameters, vital signs and ECG:

- The potentially clinically significant abnormality (PCSA) values are defined as abnormal values considered medically important by the Sponsor according to predefined criteria/thresholds based on literature review and defined by the Sponsor for clinical laboratory tests, vital signs, and ECG.

- PCSA criteria will determine which patients had at least 1 PCSA during the TEAE period, taking into account all evaluations performed during the TEAE period, including unscheduled or repeated evaluations. The number of all such patients will be the numerator for the on-treatment PCSA percentage.

The TEAE observation period is defined as the time from first dose of IMP up to 12 weeks after the last dose of IMP.

Analysis of the adverse event data

Treatment-emergent AEs, treatment-emergent SAEs, TEAEs leading to treatment discontinuation and treatment-emergent AESIs will be summarized for each treatment group based on MedDRA coding of verbatim terms reported by investigators.

Analysis of TEAE

Treatment emergent adverse event incidence tables will be presented by system organ class (SOC) (sorted by internationally agreed order), high-level group term (HLGT), high level term (HLT) and preferred term (PT), sorted in alphabetical order for each treatment group, the number (n) and percentage (%) of patients experiencing at least one TEAE. Multiple occurrences of the same event in the same patient will be counted only once in the tables within a treatment phase. The denominator for computation of percentages is the safety population within each treatment group.

Analysis of all treatment-emergent SAEs

All treatment-emergent SAEs will be presented by primary SOC, HLGT, HLT, and PT, showing number (%) of patients with at least 1 serious TEAE, sorted by SOC internationally agreed order. The other levels (HLGT, HLT, PT) will be presented in alphabetical order. Listings will be provided for all SAEs by treatment group and patient with flags indicating on-treatment status.

Analysis of all TEAEs leading to permanent treatment discontinuation

TEAEs leading to treatment discontinuation will be presented by primary SOC, HLGT, HLT, and PT, showing number (%) of patients with at least 1 TEAE leading to permanent treatment discontinuation, sorted by SOC internationally agreed order. The other levels (HLGT, HLT, PT) will be presented in alphabetical order. Listings will be provided for all TEAE leading to permanent treatment discontinuation by treatment group and patient.

Analysis of treatment-emergent AESI

Treatment-emergent AESI, by AESI category and PT, will show number (%) of patients overall, sorted by decreasing incidence of PT within each AESI category. The AESIs include, but are not limited to, the following categories and details of the MedDRA coding will be provided in the statistical analysis plan: tuberculosis, anaphylaxis, hypersensitivity, vasculitis.

Analysis of Deaths

The following deaths summaries will be generated:

- Number (%) of patients who died by study period (TEAE, on-study) and reasons for death summarized on the safety population by treatment received
- Death in nonrandomized patients or randomized and not treated patients
- TEAE leading to death (death as an outcome on the AE e-CRF page as reported by the Investigator) by primary SOC, HLG, HLT and PT showing number (%) of patients sorted by internationally agreed order of SOC and alphabetic order of HLG, HLT, and PT.

Analysis of the laboratory data

The summary statistics (including number, mean, median, standard deviation, minimum and maximum) of all laboratory variables will be calculated for each visit or study assessment (baseline, each post-baseline time point, endpoint) by treatment group. Listings will be provided with flags indicating the out of range values as well as the PCSA values.

The incidence of PCSA at any time will be summarized by treatment group for each laboratory parameter. Shift tables showing changes with respect to the baseline status will be provided.

Analysis of the vital signs data

The summary statistics (including number, mean, median, standard deviation, minimum and maximum) of all vital signs variables will be calculated for each visit or study assessment (baseline, each post-baseline time point, endpoint) by treatment group.

The incidence of PCSA at any time will be summarized by treatment group for each vital signs variable. Shift tables showing changes with respect to the baseline status will be provided. Listings will be provided with flags indicating the out of range values as well as the PCSA values.

Assessment of potential drug-induced liver injury

The liver function tests, namely ALT, AST, alkaline phosphatase and total bilirubin, are used to assess possible drug induced liver toxicity. The proportion of patients with PCSA values at any post-baseline visit by baseline status will be displayed by treatment group for each parameter. The proportion of patients with PCSA values at any post-baseline visit will also be displayed by duration of exposure for each treatment group.

A graph of distribution of peak values of ALT versus peak values of total bilirubin will also be presented. Note that the ALT and Total bilirubin values are presented on a logarithmic scale. The graph will be divided into 4 quadrants with a vertical line corresponding to 3xULN for ALT and a horizontal line corresponding to 2xULN for total bilirubin.

Summarize the normalization by parameter (to ≤ 1 ULN or return to baseline) of elevated liver function tests by categories of elevation (1-<3x, 3x, 5x, 10x, 20x ULN for ALT and AST, 1.5x ULN for Alkaline phosphatase, and 1.5x and 2x ULN for total bilirubin), with following categories of normalization: never normalized, normalized after IMP discontinuation. Note that a patient will be counted only under the maximum elevation category. 1-3, 3-5, 5-10, 10-20, >20

Summarize the incidence of liver related AEs by treatment group. The selection of PTs will be based on standardized MedDRA query (SMQ) for drug related hepatic disorders.

Analysis of the electrocardiogram data

The summary statistics (including number, mean, median, standard deviation, minimum and maximum) of all ECG variables will be calculated for each visit or study assessment (baseline, each post baseline time point, endpoint) by treatment group.

The incidence of PCSA at any during the TEAE period will be summarized by treatment group for each ECG variable. Shift tables showing changes with respect to the baseline status will be provided. Listings will be provided with flags indicating the PCSA values.

Analysis of Immunogenicity

Anti-SAR antibody (ADA) assay results will be described categorically. Descriptive statistics will be provided for:

- Patients with any positive ADA assay response during the study.
- ADA positive patients during the TEAE period.

ADA positive patient is defined as patient with at least 1 treatment-induced or treatment-boosted ADA positive sample during the TEAE period, where

- Treatment-induced ADA positive patient is defined as a patient with non-positive assay (meaning negative or unevaluable) response at baseline but with a positive assay response during the TEAE period.
- Treatment-boosted ADA positive patient is defined as a patient with a positive ADA assay response at baseline and with at least a 4-fold increase in titer during the TEAE period

The rest will be classified as ADA negative or inconclusive patients.

Response of treatment-induced ADA positive patient is further classified as transient ADA response, persistent ADA response or indeterminate.

Transient ADA response:

- Treatment-induced ADA detected only at one sampling time point during the TEAE period and at least 16 weeks before the last sample, or
- Treatment induced ADA detected at 2 or more sampling time points, where the first and last ADA positive samples (irrespective of any negative samples in between) are separated by a period less than 16 weeks and the first ADA positive sample and last ADA sample are separated by a period exceeding 16 weeks or longer.

Persistent ADA response:

- Treatment-induced ADA detected at 2 or more sampling time points during the TEAE period, where the first and last ADA positive samples (irrespective of any negative samples in between) are separated by a period exceeding 16 weeks or longer

Descriptive statistics for ADA titers will be provided for patients with positive ADA assay response and selected sub-categories.

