	
will be randomized into each treatment group, for a total sample size of approximately 300 patients for the study.
 
Analysis sets:
 
Safety analyses will be conducted on the Safety population, which includes all randomized patients who receive at least 1 injection of investigational medicinal product. Efficacy analyses will be performed on the modified intent to treat population (primary population), which includes all patients who receive at least 1 injection of investigational medicinal product, have a valid baseline % predicted FVC measurement, and have at least 1 post-baseline % predicted FVC measurement. The primary statistical analysis will be performed once all patients have completed the Week 52 assessment and the database has been cleaned and locked.
 
Primary efficacy analysis
 
A rank-based analysis of covariance (ANCOVA) will be performed on the change from baseline in % predicted FVC. The ANCOVA model will include treatment group as the main factor and the baseline % predicted FVC as a continuous covariate.
 
Analysis of secondary endpoints
 
Analysis of time to event endpoints will be performed using the log-rank test and Cox proportional hazards regression model.
 
Safety analysis
 
TEAEs and serious AEs (SAEs) (will be summarized for each treatment group by primary system organ class (SOC), high level group term (HLGT), high level term (HLT), and preferred term (PT), as well as by severity and relationship to study treatment. The rate of potentially clinically significant abnormalities (PCSAs) will also be summarized by treatment group. Additionally, listings of all AEs, SAEs, and AEs leading to treatment discontinuation will be generated. Clinical laboratory evaluations, vital signs, electrocardiograms (ECGs), a selected panel of biomarkers, and ADA will be tabulated by treatment group. These safety analyses will be compared qualitatively between the treatment groups.

DURATION OF STUDY PERIOD (per patient)
	
The study will last 68 weeks per patient as follows:
 
 • 4 weeks of screening • 52 weeks of study treatment • 12 weeks of follow-up with no study treatment

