#### *Observation period*

The observation period will be divided as follows:

- The **pre-treatment** period is defined as the time from the signed informed consent date up to the first administration of IMP.
- The **treatment-emergent adverse event (TEAE)** period is defined as the time from the first administration of the IMP to the last administration of the IMP + 84 days. It will include both **treatment** and **residual treatment** periods:
  - The **treatment** period is defined as the time from the first administration of the IMP to the last administration of the IMP + 7 days
  - The **residual treatment** period is defined as the time from the last administration of the IMP + 8 days to the last administration of the IMP + 84 days.
- The **post-treatment** period is defined as the period of time starting the day after the end of the TEAE period (ie, 85 days after the day of last dose of double-blind IMP injection).

The on-study observation period is defined as the time from the first administration of IMP until the end of the study (defined as last protocol planned visit (end of study visit) or the resolution/stabilization of all SAEs and adverse events of special interest (AESIs)).

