***Analysis of all treatment emergent serious adverse event(s)***

- All treatment-emergent serious adverse events by primary SOC, HLGT, HLT, and PT, showing the number (%) of patients with at least 1 serious TEAE, sorted by the internationally agreed SOC order. The other levels (HLGT, HLT, and PT) will be presented in alphabetical order. This table will be presented by treatment arm.
- All treatment-emergent serious adverse events by primary SOC and PT, showing the number (%) of patients with at least 1 serious TEAE, sorted by the internationally agreed SOC order and by decreasing incidence of PTs within each SOC. This table will be presented by treatment arm and by background therapy status.
- All treatment-emergent serious adverse events regardless of relationship and related to IMP, by primary SOC, HLGT, HLT, and PT, showing the number (%) of patients with at least 1 treatment-emergent serious adverse event, sorted by the internationally agreed SOC order. The other levels (HLGT, HLT, and PT) will be presented in alphabetical order. This table will be presented by treatment arm.
- All treatment-emergent serious adverse events regardless of relationship and related to IMP, by primary SOC and PT, showing the number (%) of patients with at least 1 serious TEAE, sorted by the internationally agreed SOC order and by decreasing incidence of PTs within each SOC. This table will be presented by treatment arm and by background therapy status.
- Listings will be provided for all SAEs by treatment arm during on-treatment period.

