#### ***Analysis of pre-treatment and post-treatment adverse events***

An overview presenting number of patients with any pre-/post-treatment adverse events, serious pre-/post-treatment adverse events, pre-/post-treatment adverse events leading to death, pretreatment adverse events leading to permanent treatment discontinuation will be displayed by treatment arm. If only few patients (<10% of randomized patients) are concerned, a global listing will be provided.

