#### **2.4.5.2 Deaths**

The following summaries of deaths will be generated for the safety population by treatment arm.

- Number (%) of patients who died by study period (on-study, on TEAE period, post-study) and reasons for death summarized on the safety population by treatment received and by background therapy.
- Deaths in nonrandomized patients or randomized but not treated patients
- Treatment-emergent adverse events leading to death (death as an outcome on the AE case report form page as reported by the Investigator) by primary SOC, HLGT, HLT, and PT showing number (%) of patients sorted by internationally agreed SOC order, with HLGT, HLT, and PT presented in alphabetical order within each SOC. This table will be presented by treatment received and by background therapy.
- Treatment-emergent adverse events leading to death (death as an outcome on the AE case report form page as reported by the Investigator) by primary SOC and PT showing number (%) of patients with at least 1 TEAE leading to death, sorted by internationally agreed SOC order and by decreasing incidence of PTs within each SOC. This table will be presented by treatment received and by background therapy.
- All pre-treatment adverse events leading to death by primary SOC and PT, showing the number (%) of patients, sorted by the internationally agreed SOC order and decreasing incidence of PTs within each SOC
- All post-treatment adverse events leading to death by primary SOC and PT, showing the number (%) of patients, sorted by the internationally agreed SOC order and decreasing incidence of PTs within each SOC
- Listings of deaths will be provided. For deaths in non-randomized patients or randomized and not treated patients, a distinct listing will be provided.

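### The SAP narrows the protocol's flagged listing of all SAEs to on-treatment SAEs, so non-fatal SAEs after the treatment-emergent period may be counted by arm but not identified by term

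*Protocol*

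**What the plan says.** **Protocol.** Section 11.4.3, under the analysis of treatment-emergent SAEs, states: "Listings will be provided for all SAEs by treatment group and patient with flags indicating on-treatment status". The safety paragraph of the synopsis agrees in scope: "listings of all AEs, SAEs, and AEs leading to treatment discontinuation will be generated".

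**SAP, SAE listing.** The corresponding bullet in SAP 2.4.5.1 reads: "Listings will be provided for all SAEs by treatment arm during on-treatment period". No status flag is mentioned.

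**SAP, periods.** SAP 2.1.4 fixes the treatment-emergent (TEAE) period: "period is defined as the time from the first administration of the IMP to the last administration of the IMP + 84 days". Anything with onset from day 85 after a patient's final injection counts as post-treatment.

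**SAP, post-treatment events.** The part of SAP 2.4.5.1 on pre- and post-treatment events specifies, by arm: "An overview presenting number of patients with any pre-/post-treatment adverse events, serious pre-/post-treatment adverse events, pre-/post-treatment adverse events leading to death". It then adds: "If only few patients (<10% of randomized patients) are concerned, a global listing will be provided". SAP 2.4.5.2 goes further for fatal events only: "All post-treatment adverse events leading to death by primary SOC and PT, showing the number (%) of patients".

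**The concern.** The protocol's flag serves to tell on-treatment SAEs from others within one complete listing. The SAP uses the same status to decide which SAEs are listed at all. Neither SAP 1.5 nor SAP 1.6 mentions this.

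For later events, the 10% condition runs the wrong way for serious ones: individual detail is promised when few patients are affected and not when many are.

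The data will exist. Protocol 10.3.4 follows patients who stop treatment to their scheduled end of study, and SAP 2.1.4.1 records adverse events from consent to end of study. A late infection or cancer in an early stopper could then enter the report only as one patient in a count. The protocol itself (6.3) describes safety information in IPF as sparse so far, so losing the nature of such events matters.

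**Working it through.** The plan states no figure to reproduce here. The check compares the outputs and then does simple arithmetic on study days.

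**1. Which outputs would name a non-fatal SAE occurring after the TEAE period?**

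- SAE tables by system organ class and preferred term (SAP 2.4.5.1): treatment-emergent only.
- SAE listing (SAP 2.4.5.1): on-treatment only.
- Listing of adverse events of special interest (SAP 2.4.5.1): treatment-emergent only.
- Post-treatment tables by term (SAP 2.4.5.2): fatal events only.
- Post-treatment overview (SAP 2.4.5.1): patient counts by arm, including a count for serious events, without terms.
- Global listing (SAP 2.4.5.1): names the events, but only below the 10% threshold.
- Exacerbation description and hospitalization summary (SAP 2.4.4.2.3.1 and 2.4.4.2.3.2): randomization to Day 375, regardless of the TEAE period. The first gives preferred term and verbatim for diagnoses other than exacerbation. The second is accompanied by a listing of reasons.

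Only the last two items can supply a term or reason. One is conditional and the other partial.

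**2. Threshold.** About 300 patients are randomized (SAP 1.3). 0.10 × 300 = 30, so the listing is promised for at most 29 patients. The SAP does not say whether pre-treatment events count toward the same 10%. If they do, the limit is reached sooner.

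**3. Follow-up outside the TEAE period.** Inputs are the target days in SAP Table 6 (Week 52 = Day 365, Week 64 = Day 449), the 84-day rule in SAP 2.1.4 and the Day 375 cut-off. The formulas are:

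- last-dose day = 7 × week + 1
- TEAE end = last-dose day + 84
- post-TEAE days = 449 − TEAE end

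| Last dose | Day | TEAE end | Post-TEAE days | To Day 375 | After Day 375 |
|---|---|---|---|---|---|
| Week 12 | 85 | 169 | 280 | 206 | 74 |
| Week 24 | 169 | 253 | 196 | 122 | 74 |
| Week 36 | 253 | 337 | 112 | 38 | 74 |
| Week 48 | 337 | 421 | 28 | 0 | 28 |
| Week 52 | 365 | 449 | 0 | 0 | 0 |

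The gap falls on early stoppers who remain in follow-up. The exacerbation and hospitalization outputs cover at most the fifth column.

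**4. When would the listing lapse?** The documents give no discontinuation rate, so the following is a range of assumptions. If 15%, 20% or 30% stop early (45, 60 or 90 patients), 30 patients are reached when 30/45 = 67%, 30/60 = 50% or 30/90 = 33% of them have a post-treatment event.

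**5. Illustration of volume.** Suppose 20–30% stop at a mean of Week 26 and all stay to Week 64. Each then has 64 − (26 + 12) = 26 post-TEAE weeks. That gives 60 × 26 = 1,560 to 90 × 26 = 2,340 weeks, about 30–45 patient-years. Total follow-up is 300 × 64 = 19,200 weeks (about 368 patient-years), so the share is 8–12%. This is follow-up time at risk of the gap, not time certain to be unlisted.

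**6. Meaning of on-treatment.** For deaths (SAP 2.1.4.2) and for potentially clinically significant abnormalities (SAP 2.4.5) it means the TEAE period. For last and worst values (SAP 2.4.5) it means the treatment period, last dose + 7 days. The two readings differ by 84 − 7 = 77 days for the SAE listing.

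**The case against.** **The protocol sentence may be narrower than it looks.** It stands under a heading on treatment-emergent SAEs, so it could mean all SAEs of that section. This is possible but not the natural reading. Protocol 11.4.3 itself ties on-treatment to the TEAE period when it defines the abnormality percentages. On that meaning, a flag within treatment-emergent SAEs would be the same for every row. The synopsis also promises all SAEs without restriction.

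**Non-declaration is weak evidence.** SAP 1.5 covers major changes, and the scope of one listing need not count as major. This stands, and the point does not depend on it.

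**Other text points to fuller reporting.** The opening of SAP 2.4.5.1 says pre- and post-treatment events are described separately and sets a sort order across all periods. Protocol 10.5 and 10.7 require safety observations and events in the study report. However, the specific SAP section defines only the overview and the conditional listing. The protocol's general duty shows the SAP is too narrow; it does not supply the missing output.

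**A reader might infer that a delayed safety signal would be invisible.** The documents do not support that. The overview gives patients with serious post-treatment events by arm, so an imbalance would show. Expedited SAE reporting and the Data Monitoring Committee also operate during the trial. What may be missing is which events they were.

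**A reader might infer that completers lose 77 days of SAE reporting.** On the +7-day reading they would drop out of the patient listing for that interval. Their SAEs on days 8–84 would still appear in the treatment-emergent tables by preferred term.

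**The volume figures are assumed and lean high.** This stands. SAP 2.2 foresees patients leaving the study before Week 52 after 12 weeks of follow-up, and they would add little post-TEAE time. Below 30 patients the global listing names the events and the loss disappears.

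**Conclusion.** The protocol and SAP differ on which SAEs are listed, and the SAP's conditional listing does not reliably make up the difference. Non-fatal SAEs after the TEAE period may be counted by arm but not identified by term, except where the exacerbation or hospitalization outputs capture them.

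This can arise only for patients who stop treatment early and stay in follow-up, and it is certain to be avoided only if fewer than 30 of about 300 patients are concerned. The days per patient follow from the documents. The number of patients does not, so any patient-year total is illustrative.

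The primary and secondary analyses, the treatment-emergent tables, the death outputs and the data collection are unaffected. Severity is minor to moderate.

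**What to change.** 1. In SAP 2.4.5.1, replace the SAE listing bullet with a listing of all SAEs from informed consent to end of study, by arm and patient, flagged as pre-treatment, treatment, residual-treatment or post-treatment. Starting at consent matters: a listing that began at first dose would still fall short of the protocol's all SAEs. The four-way flag also removes the doubt over what on-treatment means.
2. In the SAP section on pre- and post-treatment events, make the listing of serious post-treatment events unconditional. Keep the 10% condition for non-serious events only, and say whether pre-treatment events count toward it.
3. If the sponsor prefers the narrower listing, record and justify that departure in SAP 1.5.

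The cost is SAP wording and a longer listing from data already collected. No new data or analysis is needed.
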